Appendix I

Screening information and selection of cases

Last name: ----- **First name:** -----

Date: -----

Date of Birth: ----- (YY/ MM / DD)

Email address: _____@_____.

RVH/MGH # -----

Assigned ID code: _____ - _____ - _____ (MGH/RVH – Initials – # on envelope)

(Fill ID code out later at time of SHGNB)

INCLUSION CRITERIA	YES	No
Referral for UAE		Exclude
Ability to comply with the requirements of the study procedures.		Exclude
Subject expected to be able to give consent at time of UAE?		Exclude
EXCLUSION CRITERIA		
Patient with abnormal anatomy on MRI in which the aortic/IVC bifurcations are not normally seated and cannot be used to assess the position of the SHGN plexus?	Exclude	
Allergy to local anesthetic agent?	Exclude	
Skin abnormality in the periumbilical region that preclude placement of a needle through this area?	Exclude	
Untreated infection at time of UAE?	Exclude	
History of IBD or Colitis?	Exclude	
Abnormal anticoagulation status?	Exclude	
Pre-existing conditions, which, in the opinion of the investigator, interfere with the conduct of the study?	Exclude	
Uncooperative patient or cannot follow instructions, or who is unlikely to return to get the filter removal due to poor compliance to follow-up medical appointments?	Exclude	
Mental state that can preclude completion of the study?	Exclude	

Pre UAE MRI review:

of fibroids (1/2/3/>3): _____

Size of three largest fibroid – (save image on PACS with fibroids labeled)

1) _____ x _____ x _____ (cm) % necrosis: _____

2) _____ x _____ x _____ (cm) % necrosis: _____

3) _____ x _____ x _____ (cm) % necrosis: _____

% necrosis overall: _____

Adenomyosis: No Yes: Focal Diffuse

Ovarian anastamosis: No

Ovarian anastamosis: No
 Left
 Right

Primary symptom from fibroids:

- Menorrhagia
- Bloating
- Increased urinary frequency
- Constipation
- Dyspaneuria
- Other: _____

Attach Patient's UFS-QOL questionnaire

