
Study Rationale
	
Uterine fibroids have a significant negative impact on the quality of life of many women who are in their reproductive years. Problems associated with uterine fibroids include excessive blood loss during menstruation (menorrhagia) with often irregular menstrual periods (menometrorrhagia), in some cases leading to marked anemia and need for blood transfusions, excessive pain especially during menstruation (dysmenorrhea), and symptoms of bulk causing compression on the bladder and increased urinary frequency often with waking up at night to urinate (nocturia) or even incontinence, or compression of the rectum causing constipation. As well many women suffer from painful intercourse (dyspareunia), which can have negative impact on self-image and marital status. These symptoms can be very debilitating, and are often career limiting.
 
Until relatively recently, most of these women had to opt for hysterectomy to help control these symptoms. However in the late 1990s, several publications demonstrated the feasibility of uterine artery embolization to control these symptoms. By blocking the blood flow to the fibroids, the fibroids became necrotic and the symptoms resolved. Since then the technique has become widely accepted as a less invasive alternative to surgery with excellent clinical results.

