Exclusion Criteria	
 1. Patients in whom the vascular anatomy prevents access to the superior hypogastric nerve plexus safely 2. Patients who have known allergy to the anesthetic agent 3. Patients with signs of skin infection at the entry site of the needle used to place the nerve block 4. Patients with signs of infection such as fever 5. Patients with history of inflammatory bowel disease or with signs of colitis 6. Patients with uncorrectable abnormal coagulation status (INR >1.5 and plt < 50000 without use of anticoagulation agents) 7. Patients with preexisting conditions, which, in the opinion of the investigator, interfere with the conduct of the study. 8. Patients who are uncooperative, cannot follow instructions, or who is unlikely to comply with follow-up appointments or fill-out the post-procedural pain questionnaires. 9. Patients with mental state that may preclude completion of the study procedure or be unable to provide informed consent
Schedule of Study Visits	
No change from routine schedule presently used:
 
 1) MRI pre-UAE 2) Consultation pre-UAE (consent will be obtained at this time) 3) UAE procedure (not usually the same day as the consultation) 4) MRI 4-6 months post-UAE 5) Consultation post-UAE after post-UAE MRI completed
Efficacy Outcome	
 ▪ Primary: 
 ○ Reduction in pain as measured by patient self administration of visual analogue scale

	
 ○ Reduction in use of oral analgesics at home and IV/oral analgesics while in hospital ▪ Secondary: Comparison of sham versus SHGNB group to look for 
 ○ Differences in adverse events ○ Differences in pain/complication related admissions ○ Differences in pain in relation to total volume of fibroids ○ Differences in pain in relation to fibroids versus adenomyosis ○ Differences in successful outcome of the embolization both by imaging and clinically ○ Use of the online questionnaire vs the paper questionnaire

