1.0 Background

1.1. Uterine Fibroids

Uterine fibroids are a monoclonal tumor of smooth muscle origin. Their cause is unknown but is known to be hormone responsive, being diagnosed only after menarche and decreasing after menopause [1].

Uterine fibroids are the most common pelvic tumors in women being present in >80% of black women and approaching 70% in white women in their late 40s. Of these, 50% of black women and 35% of white women have clinical symptoms caused by the fibroids [1]. In 2008-2009, the estimated rate of hysterectomies in Canada was 338/100000 women > 20 years old, with an estimated \$192 million dollars in associated hospitalization costs (Canadian Institute for Health Information). Of these, abnormal menstrual bleeding and fibroids remain the most common reason for hysterectomies. The most common clinical symptoms associated with fibroids are increased bleeding during menstruation, increased pelvic pain especially during menstruation or sexual intercourse, and pressure effects on surrounding structures causing increased urinary frequency and constipation. These symptoms can be very debilitating.

Fibroids are almost exclusively benign in nature. However they can be difficult to differentiate from malignant sarcomas. Fortunately such sarcomas are rare, being estimated at 0.2% or less in surgical series [2].

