Because of the success of the group in Ottawa in performing the SHGNB, we have just recently started to offer this procedure as well. Initial results are also very encouraging with recovery nurses informing us that in general the patients seem to be doing much better with the nerve block in place. However the data remains anecdotal. There have been no studies to date comparing simple oral/IV sedation to SHGNB + oral/IV sedation. For this reason, probably, the procedure has been very slow to be adopted by people who perform UAEs. We believe that, to put this issue to rest, there is a necessity for such a comparative trial and, especially important in the context of a subjective outcome such as pain, it is our belief that a randomized double-blinded control trial is needed to obtain conclusive data. This was the reason this study was put together.

2. Research Question:

Is there a difference in subjective pain score patients experience and in the need for analgesics post uterine artery embolization for fibroids if the patients undergo a superior hypogastric nerve block during the embolization procedure.

3. Objectives:

The primary objective is to assess:

- Reduction in subjective pain as measured by patient self administration of visual analogue scale and reduction in use of oral analgesics at home and IV/oral analgesics while in hospital

The secondary objectives are:

- Differences in adverse events between groups with and without SHGNB
- Differences in pain/complication related admissions between groups with and without SHGNB
- Differences in pain in relation to total volume of fibroids between groups with and without SHGNB
- Differences in pain in relation to fibroids vs. adenomyosis between groups with and without SHGNB
- Differences in successful outcome of the embolization both by imaging and clinically between groups with and without SHGNB
- Differences in admission rates
- Differences in rates of return visits to ER for pain issues
- Patient use and appreciation of the online pain survey

4. Implications:

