Subject data collection at the time of enrollment will include demographics, relevant medical history and vital signs. Subjects will be followed-up as outlined in Table 1 to assess adverse events related to the procedures and clinical success of the procedure. Individual data collection will be considered complete at the time of the follow-up consultation 4-6 months after the UAE procedure.

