7.3. Visit on day of Consult

The following should be done at the initial visit:

- Obtain consent for the uterine fibroid embolization procedure
- Review protocol specific inclusion and exclusion criteria.
- Assess whether patient is able to provide consent or not. If the patient is appropriate for the study, informed consent is obtained. This consent will be obtained by an interventional radiologist who will not be involved in the procedure itself.
- Obtain relevant medical history and current demographic data.

Presence of inclusion criteria and absence of exclusion criteria will be verified on the designated source documents and eCRF.

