Appendix II - At time of UAE

Identification code: _____

Date of UAE: _____ (YY/ MM / DD)

RVH/MGH # _____ Age: _____

Do not open envelope until ready to do block (i.e. when switch doctors)

Consent signed: Yes No (do not proceed)

UAE PROCEDURAL DETAILS (to be filled by UAE IR without knowledge of Randomization group):

Pain scale at start of procedure (0-10): _____ (time: __:__)

Embolization material and size used: _____

Arteries embolized:

	Rt UA	# vial of PVA: _____
	Lt UA	# vial of PVA: _____
	Rt OA	# vial of PVA: _____
	Lt OA	# vial of PVA: _____

Other: _____ # vial of PVA: _____

Total fluoroscopy time of entire procedure: _____

Ovarian artery anastamosis seen?

No
 Left
 Right

Complications during UAE:

Pain (scale 1-10: _____)
 Arterial spasm - artery: _____
 Extravasation - artery: _____
 Groin hematoma

Other: _____

How many sites of injections: 1 or 2 or >2

Immediate complications from SHGNB/SHAM procedure:

Pain - where: _____

Bleeding

Rigors/Fever

Other: _____

IR UAE: _____ IR SHGNB: _____

Technologist: _____

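### Analgesic use is one of the two primary outcome items, but no form shown asks about usual analgesic use before the procedure, so some precision in that comparison is given up unnecessarily

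*Combined protocol and SAP*

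**What the plan says.** The synopsis (Efficacy Outcome) lists two primary items: pain on a visual analogue scale, and "Reduction in use of oral analgesics at home and IV/oral analgesics while in hospital". Section 3 repeats both.

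At baseline, Section 7.1 states: "Subject data collection at the time of enrollment will include demographics, relevant medical history and vital signs". Section 7.3 has a similar line for the consult: "Obtain relevant medical history and current demographic data". Table 1 schedules history and examination at the consult and again on the procedure day. None of these says that analgesic use is to be asked about.

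The forms record the following:

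- **Appendix I (screening):** eligibility, MRI findings, and a "Primary symptom from fibroids" list with five named symptoms and a free-text line. The UFS-QOL is attached. There is no analgesic field.
- **Appendix II (procedure):** a pain score, "Pain scale at start of procedure (0-10", but no prior medication.
- **Appendix III (recovery):** drugs given in recovery and prescribed at discharge.
- **Appendix V (follow-up):** no analgesic field.
- **Home sheets (Section 7.5):** pain and medication, only after the procedure and up to day 10.

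None of the nine exclusion criteria names regular analgesic or opioid use. Only the general investigator-opinion criterion could reach it. Section 8 plans a Student's t-test for continuous variables. The regression and ANOVA methods mentioned there and in Section 5 name no baseline covariate.

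**The concern.** Many women referred for embolization have pain already. Section 1.1 counts "increased pelvic pain especially during menstruation or sexual intercourse" among the most common fibroid symptoms. A woman who regularly takes analgesics may go on taking them afterwards, and the home sheets would count those tablets with the ones taken for post-embolization pain. Variation in prior habit therefore enters a primary outcome as noise.

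A recorded baseline would let the analysis remove part of that noise and let a reader see whether regular users fell unevenly between two small arms. Without a standardized question, neither can be done dependably. The protocol states no power for analgesic use, so there is no known margin to absorb the loss.

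**Working it through.** **The plan's own figure.** The only sample-size figure is for pain: a drop from 7 to 5 with SD 2.5, so d = 2/2.5 = 0.8, giving 42 in total. A one-sided two-sample t-test at 0.05 with 80% power needs 20.03 per arm, rounded up to 21, or 42 in total, so the figure reproduces on that basis. The two-tailed rule in Section 8 would give 26 per arm, or 52; that is a separate matter. No effect size or SD is given for analgesic use, so the working below is in relative terms.

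**Completers.** 50 enrolled (25 per arm) with 20% dropout: 50 × 0.8 = 40, or 20 per arm.

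**Precision.** Adjusting for a baseline that correlates at r with the outcome leaves a fraction 1 − r² of the variance. The 40 completers are then worth 40/(1 − r²) unadjusted ones, ignoring the one degree of freedom spent. The value of r is an assumption.

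| r (assumed) | Variance removed (r²) | 40 completers worth |
|---|---|---|
| 0.2 | 4% | 40/0.96 = 41.7 |
| 0.3 | 9% | 40/0.91 = 44.0 |
| 0.4 | 16% | 40/0.84 = 47.6 |

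**Is that range of r sensible?** Treat regular use as yes/no with prevalence p, and let users' outcome lie d within-group SDs above non-users'. Then r = d√(p(1 − p)) / √(1 + d²p(1 − p)). With d = 1:

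- p = 0.10: r = 0.30/√1.09 = 0.29
- p = 0.20: r = 0.40/√1.16 = 0.37

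To reach r = 0.6, d²p(1 − p) must equal 0.36/0.64 = 0.5625. That needs d = 0.75/0.30 = 2.5 at 10% prevalence, or 0.75/0.40 = 1.9 at 20%. Shifts of that size have no support in the documents, so 0.2 to 0.4 is the range to use.

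**Chance imbalance.** Let the number of regular users in each arm be binomial(n, p). The exact probability that the arms differ by three or more users, in either direction, is:

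| Per arm | p = 10% (assumed) | p = 20% (assumed) |
|---|---|---|
| 20 | 18% | 32% |
| 25 | 23% | 37% |

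**What such an imbalance does.** With three more users in one arm of 20 and a 1-SD shift in users, the arm difference moves by (3/20) × 1 = 0.15 SD.

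**The case against.** The strongest reply is that a randomized comparison needs no baseline. The t-test is valid as planned, and ordinary chance imbalance is already reflected in its standard error. That stands: a reader might infer bias or an invalid test, and the documents support neither.

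The second reply is that the information may be collected anyway. History is taken at the consult and on the procedure day, and Section 7.3 refers to source documents and an eCRF that are not reproduced. Appendix I also lacks a vital-signs field although Section 7.1 promises vital signs, so its silence does not prove that an item goes unrecorded. This stands in part. It would be too strong to say that prior use can never be recovered. But an unprompted history is not a standardized variable, and nothing in the plan says it will be used.

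Third, pain itself is not without a baseline. Appendix II takes a 0-10 score at the start of the procedure, the UFS-QOL is completed at the first consultation (its items are not reproduced, so its content cannot be checked), and dysmenorrhea can be written on the free-text symptom line. A reader might take the missing pelvic-pain box as a defect in the pain outcome; no effect of it on the pain comparison can be shown.

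Fourth, all women go home on a standard prescription and recovery dosing follows a set escalation scheme. Shared scheduled dosing could weaken the link between prior habit and later use. That is fair, and it argues for the lower end of the range of r.

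**Conclusion.** The point holds as a modest one about precision. A primary outcome item is analgesic use, no form shown has a defined field for usual use, no exclusion removes regular users, and no baseline covariate is named.

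The size rests on two assumptions that the documents cannot supply. With r of 0.2 to 0.4, adjustment is worth about 2 to 8 extra completers on 40. With 10% to 20% regular users, an imbalance of three or more occurs in roughly a fifth to a third of trials with 20 per arm, and moves the arm difference by about 0.15 SD if users sit 1 SD higher.

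Two larger readings should be resisted. Home use is not half of the primary outcome; it is one component of the second item, pooled with in-hospital use. And gains such as 40 completers being worth 53 or 62 require r of 0.5 to 0.6, which fits poorly with a prevalence of 10% to 20%. Severity is low.

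**What to change.** 1. Add one standardized question to Appendix I, answered before randomization: regular analgesic or opioid use, yes or no, and if yes, days per month.
2. In Section 8, compare analgesic use between arms with a linear model (ANCOVA) that includes one prespecified variable from this question. Days per month, set to zero for non-users, would serve and needs no dose conversion. The model also needs a stated summary measure of analgesic use, which the plan does not yet define.
3. For the pain comparison, use as covariate the 0-10 score at the start of the procedure, which Appendix II already collects before the block or sham. A pelvic-pain box on Appendix I is optional.

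The cost is about a minute of interview and one degree of freedom per model. Eligibility and treatment do not change.

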Appendix II - At time of UAE

Identification code: _____

Date of UAE: _____ (YY/ MM / DD)

RVH/MGH # _____ Age: _____

Do not open envelope until ready to do block (i.e. when switch doctors)

Consent signed: Yes No (do not proceed)

UAE PROCEDURAL DETAILS (to be filled by UAE IR without knowledge of Randomization group):

Pain scale at start of procedure (0-10): _____ (time: __:__)

Embolization material and size used: _____

Arteries embolized:

	Rt UA	# vial of PVA: _____
	Lt UA	# vial of PVA: _____
	Rt OA	# vial of PVA: _____
	Lt OA	# vial of PVA: _____

Other: _____ # vial of PVA: _____

Total fluoroscopy time of entire procedure: _____

Ovarian artery anastamosis seen?

No
 Left
 Right

Complications during UAE:

Pain (scale 1-10: _____)
 Arterial spasm - artery: _____
 Extravasation - artery: _____
 Groin hematoma

Other: _____

How many sites of injections: 1 or 2 or >2

Immediate complications from SHGNB/SHAM procedure:

Pain - where: _____

Bleeding

Rigors/Fever

Other: _____

IR UAE: _____ IR SHGNB: _____

Technologist: _____

Appendix III - At discharge from recovery room

Identification code: _____

Date of UAE: _____ (YY/ MM / DD)

RVH/MGH # _____ Age: _____

Pain scale at time of arrival to recovery (0-10): _____ (time: __:__)

IV Medications used during recovery (Dose/ time/pain scale at time of giving it):

Fentanyl (Dose/Time): _____ ug _____:_____ /10
 _____ ug _____:_____ /10
 _____ ug _____:_____ /10
 _____ ug _____:_____ /10
 _____ ug _____:_____ /10

Midazolam (Dose/Time): _____ mg _____:_____ /10
 _____ mg _____:_____ /10
 _____ mg _____:_____ /10
 _____ mg _____:_____ /10
 _____ mg _____:_____ /10

Other (Name/Dose/Time): _____ :_____ /10
 _____ :_____ /10
 _____ :_____ /10

Oral Medications used during recovery (Dose/time/pain scale at time of giving it):

Empracet: _____ / _____ : _____ / _____ /10
 Tramacet: _____ / _____ : _____ / _____ /10
 Oxycodone: _____ / _____ : _____ / _____ /10
 Hydromorphone: _____ / _____ : _____ / _____ /10
 Naprosyn: _____ / _____ : _____ / _____ /10
 Other: : _____ / _____ : _____ / _____ /10
 _____ / _____ : _____ / _____ /10

Pain scale at departure from recovery (0-10): _____ (time: __:__)

Admission to hospital

No Yes - Why: _____

Complications while in recovery: _____

Patient D/C with antibiotics No
 Yes (Name/Dosage/Frequency x # Days)
_____ / _____ / _____ x _____ d

Patient D/C meds: (Name/Dosage/Frequency x # Days)

- Empracet / _____ / _____ x _____ d
- Tramacet / _____ / _____ x _____ d
- Oxycodone / _____ / _____ x _____ d
- Hydromorphone / _____ / _____ x _____ d
- Naprosyn / _____ / _____ x _____ d

Other: _____ / _____ / _____ x _____ d
_____ / _____ / _____ x _____ d
_____ / _____ / _____ x _____ d

Inform patient how to fill out pain scales at home and how to do it by internet. Give out the sheets but encourage using internet if possible and patient at ease with this.

If willing to use internet:

Get patient email address: _____@_____.

Patient anonymous login name: _____

(first letter of hospital/tree numbers in assigned ID code (Ex if first patient enrolled and at the RVH – anonymous ID # is R001))

Give out their login name for the anonymous internet access and write down on hard copy pain scale sheets that go with patient. Give out hard copy sheets even if patient wants to use internet.

Send email immediately to patient to link to internet forms.

Appendix IV - Sheets to be filled out by patient

We encourage you to fill out these sheets via the internet if possible using the following anonymous login name and password to sign in. Otherwise you can use these hard copies and mail them back to us in the prestamped envelope or bring them back to your follow-up visit in 4-6 months.

You will receive an email giving you a link to the internet forms

Your anonymous login name for the internet is: _____

Your Password is: _____

Appendix V - At follow-up consult

Post UAE MRI review:

of fibroids (1/2/3/>3): _____

Size of three largest fibroid labeled on pre UAE consult

1) _____ x _____ x _____ (cm) % necrosis: _____

2) _____ x _____ x _____ (cm) % necrosis: _____

3) _____ x _____ x _____ (cm) % necrosis: _____

% necrosis overall: _____

Adenomyosis No Yes: Focal Diffuse

% necrosis of adenomyosis: _____

Ovarian anastamosis: No
 Left
 Right

Complications since the UAE:

Persistent Pain - Where: _____

Arrested periods - Since when: _____

Vaginal bleeding outside of periods

Symptoms of peri-menopause (hot flushes, nights sweats, etc)

Since when: _____

Endometritis - treated when: _____

Other infection – where: _____ treated when: _____

Need for surgery - When: _____

Why: _____

Continued symptoms as they were before the UAE (no clinical improvement)

Other: _____

Clinical outcome of UAE:

- Complete resolution of symptoms
- >80% improvement in symptoms
- 50-80% improvement in symptoms
- 20-50% improvement in symptoms
- <20% improvement in symptoms

Is patient happy with the outcome (scale 0-10): _____

Attach Patient's UFS-QOL questionnaire

Appendix VI - UFS-QoL questionnaire

See: Spies et al. 2002. The UFS-QOL, a new disease-specific symptom and health-related quality of life questionnaire for leiomyomata. *Obstet Gynecol.* 99(2):290-300.
